14.1.2 Sensitivity Analyses

A sensitivity analysis will be conducted in which the start of any other anti-cancer treatment or procedure prior to study discontinuation will be considered as PD, and any subsequent tumor assessments will not be considered in the objective response assessment. If only partial dates are known for the start of other anti-cancer treatment or procedures, the imputation rules described in Section 9.8 should be followed.

14.1.3 Futility Analysis

Best Overall Response (BOR) as described above will be reported for the first 12 participants, in Cohort A. If there are less than 2 responders (confirmed CR or PR) the enrollment of 2nd line participants for the study might be stopped for futility.

14.1.4 Subgroup Analyses

Subgroup analyses will be performed on the primary endpoint by cohort and assigned dose level of tepotinib for all the baseline subgroup levels defined in Section 8.2. All the subgroup analyses are exploratory and no adjustment for multiplicity will be performed. In case of low number of participants within a subgroup level (< 5 participants), levels will be pooled when meaningful.

For each subgroup, the BOR, the number of participants achieving objective response, and the ORR along with the two-sided exact Clopper-Pearson 95% CIs will be presented.

In addition to the presentation in summary tables, forest plots will be created to graphically present ORRs and corresponding 95% CIs.

14.2 Secondary Endpoints

14.2.1 Duration of Response

Duration of Response (DoR) as assessed by Investigator will only be evaluated in participants with objective response (as defined in Section 14.1.1).

DoR is the time from when the CR/PR (whichever is first) criteria are first met until PD or death due to any cause within the period of 2 scheduled tumor assessments (84 or 168 days) after the last tumor assessment, whichever occurs first (see Eisenhauer EA, et al 2009) (i.e. date of PD/death - date of last evaluable tumor assessment \leq 84 or 168).

DoR data will be censored on the date of the last evaluable tumor assessment for participants who do not have an event (PD or death) or for participants with an event after the period of 2 scheduled tumor assessment (more than 84 or 168 days) after the last evaluable tumor assessment (i.e. date of PD/death

- date of last evaluable tumor assessment > 84 or 168). Participants who do not have a tumor assessment after objective response will be censored at the date CR/PR criteria are first met.

The last evaluable tumor assessment is defined as the last tumor assessment result that is not “NE”.

Kaplan-Meier estimates (product-limit estimates) will be presented together with a summary of associated statistics for duration of response: median and corresponding two-sided 95% confidence interval (CI), Q1 and Q3, minimum and maximum. DoR rate estimates at 3, 6, 9, 12, 15, 18 months and for every 3 months thereafter as applicable including the corresponding two-sided 95% CIs will also be reported. The CI for the median will be calculated according to Brookmeyer and Crowley (1982) and CIs for the survival function estimates at the above defined time points will be derived using the log-log transformation according to Kalbfleisch and Prentice (1980) (conftype=loglog default option in SAS Proc LIFETEST). The estimate of the standard error will be computed using Greenwood's formula. Kaplan-Meier plots will also be presented.

Time to and duration of response as assessed by Investigator for every participant will be plotted using a swimmer plot. Symbols color coded will be used to show the time of the following events: complete response, partial response, progressive disease, death, ongoing response and end of treatment.

Estimand Attributes

Endpoint:

- DoR according to RECIST 1.1 as assessed by Investigator, measured by time from first documentation of objective response to PD or death, occurring within 2 scheduled tumor assessments (84 or 164 days, respectively) after last evaluable assessment or first dose

Population:

- Participants with *RAS/BRAF* wild-type left-sided metastatic colorectal cancer (mCRC) having acquired resistance to anti-EGFR antibody targeting therapy due to *MET* amplification

Treatment:

- Tepotinib combined with cetuximab

Intercurrent Event Strategy:

- Discontinuation of treatment (treatment-policy strategy, i.e. regardless of the intercurrent event)
- Start of subsequent anti-cancer treatment (treatment-policy strategy, i.e. regardless of the intercurrent event)
- Death within two scheduled tumor assessments after last evaluable assessment will be considered as event of interest (composite strategy)

Population Level Summary:

- Kaplan-Meier estimates

Follow-up for duration of response

In order to assess the follow-up for duration of response, Kaplan-Meier estimates will be calculated using the censoring rules with reverse censoring indicator.

Kaplan-Meier estimates (product-limit estimates) will be presented in the same way as in the analysis described above for duration of response.

The following information will also be presented:

- Number of participants with Objective Response (confirmed CR/PR)
- Number of responders (confirmed CR/PR) with duration of response: ≥ 6 months / ≥ 9 months / ≥ 12 months
- Number of responders (confirmed CR/PR):
 - with ≥ 6 months follow-up from onset of response (CR, PR or SD) or event (PD or death) or who discontinued treatment < 6 months after onset of response
 - Ongoing response with < 6 months duration, on treatment

14.2.2 Progression Free Survival

Progression Free Survival (PFS) time as assessed by Investigator is defined as the time (in months) from first administration of study intervention to the date of the first documentation of PD or death due to any cause, whichever occurs first if only the event happened within the period of 2 scheduled assessments (84 or 168 days) after the last tumor assessment (i.e. time between date of PD/death - date of last evaluable tumor assessment ≤ 84 or 168 days). The tumor response will be determined according to RECIST 1.1. and assessed by the investigator.

PFS data will be censored on the date of the last evaluable tumor assessment for participants who do not have an event (PD or death) or for participants with an event after the period of 2 scheduled tumor assessments (84 or 168 days) after the last tumor assessment (i.e. date of PD/death - date of last evaluable tumor assessment > 84 or > 168 days).

The last evaluable tumor assessment is defined as the last tumor assessment result that is not “NE”.

Participants who do not have a baseline tumor assessment or who do not have any post baseline tumor assessments will be censored at the date of the start of study intervention.

Participants who do not have an evaluable post-baseline tumor assessment will be censored at the date of the start of study treatment unless death occurred within the period of 2 scheduled tumor assessments (84 or 168 days, respectively) after the first dose of study treatment in which case the death will be considered an event.

The censoring and event date options to be considered for the PFS are presented in [Table 5](#).

Table 4. Date of event / censoring definition for PFS analysis

Status		Censoring	Date of event / censoring
Progressed or died	Within the period of 2 scheduled tumor assessment (84 or 168 days, respectively) after last response assessment of CR, PR or SD or start of treatment	Event	Minimum (Date of PD, Date of death)
	Otherwise	Censored	Date of last tumor assessment with outcome CR, PR or SD or date of start of treatment, whatever is later
Neither progressed nor died		Censored	Date of last tumor assessment with outcome CR, PR or SD or date of start of treatment, whatever is later

CR = Complete Response, PR = Partial Response, SD = Stable Disease, PD = Progressive Disease.

Kaplan-Meier product-limit estimates will be presented together with a summary of associated statistics for PFS: median and corresponding two-sided 95% confidence interval (CI), Q1 and Q3, minimum and maximum. Progression-free rate estimates at 3, 6, 9, 12, 15, 18 months and for every 3 months thereafter as applicable including the corresponding two-sided 95% CIs will also be reported. The CI for the median will be calculated according to Brookmeyer and Crowley (1982) and CIs for the survival function estimates at the above defined time points will be derived using the log-log transformation according to Kalbfleisch and Prentice (1980) (conftype=loglog default option in SAS Proc LIFETEST). The estimate of the standard error will be computed using Greenwood's formula. Kaplan-Meier plots will also be presented.

Estimand Attributes

Endpoint:

- Progression-free survival time, defined as the time from first dose until PD according to RECIST 1.1 or death events occurring within two scheduled tumor assessments after last evaluable assessment or first dose

Population:

- Participants with *RAS/BRAF* wild-type left-sided metastatic colorectal cancer (mCRC) having acquired resistance to anti-EGFR antibody targeting therapy due to *MET* amplification

Treatment:

- Tepotinib combined with cetuximab

Intercurrent Event Strategy:

- Discontinuation of treatment (treatment-policy strategy, i.e. regardless of the intercurrent event)
- Start of subsequent anti-cancer treatment (treatment-policy strategy, i.e. regardless of the intercurrent event)

- Death within two scheduled tumor assessments after last evaluable assessment will be considered as event of interest (composite strategy)

Population Level Summary:

- Kaplan-Meier estimates

Follow-Up Duration of PFS

In order to assess the follow-up duration of PFS, Kaplan-Meier estimates will be calculated using the censoring rules with the reverse censoring indicator.

Kaplan-Meier estimates (product-limit estimates) will be presented in the same way as in the analysis described above for PFS.

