Activity / Assessment	Screening / Baseline	Intervention Period (in cycles of 3 weeks)									EoT	Safety Follow up / Discontinuation	Survival Follow-Up / EoS / 1-Year Follow-Up	Notes
	Day -56 to Day -1	Cycle 1 (21 days)		Cycle 2 (21 days)		Cycle 3 and subsequent cycles (21 days)		Within 14 days after decision to withdraw IMP	30 days after the last dose	After Safety Follow-Up, every 3 months, up to 1-year Site Visit or by Telephone				
Cycle Day		1	8	15	1	8	15	1	8	15				
Visit Window		± 3 days			± 3 days			± 3 days				- 3 to + 7 days	± 1 month	
ctDNA sample	X							Cycle 3, 5, 9 and 13 only			X			Collection predose (within 60 min prior to tepotinib dose), before premedication, if applicable (See Appendix 4)
Documentation of RAS/BRAF wild-type status, and high MET amp levels	X													Confirmed prior to enrollment and after disease progression on the previous anti-EGFR therapy by an established test.
Tepotinib until PD or intolerance		QD												Decided by the Sponsor and SMC: Dosing may be stopped at any time to review safety and PK data and allow for adjustments before dosing is resumed. Additional schedules may also be evaluated.
Cetuximab until PD or intolerance		Weekly (Day 1)												See Section 6.1 for details of premedication required prior to first infusion.

Activity / Assessment	Screening / Baseline	Intervention Period (in cycles of 3 weeks)									EoT	Safety Follow up / Discontinuation	Survival Follow-Up / EoS / 1-Year Follow-Up	Notes
	Day -56 to Day -1	Cycle 1 (21 days)		Cycle 2 (21 days)		Cycle 3 and subsequent cycles (21 days)		Within 14 days after decision to withdraw IMP	30 days after the last dose	After Safety Follow-Up, every 3 months, up to 1-year Site Visit or by Telephone				
Cycle Day		1	8	15	1	8	15	1	8	15				
Visit Window		± 3 days		± 3 days		± 3 days			- 3 to + 7 days		± 1 month			
Tumor Assessment (RECIST Version 1.1) based on MRI and/or CT scans and other protocol-defined imaging modalities.	X							X #)					See Section 8.1 Screening tumor assessment needs to happen within 28 days prior to dosing. All evaluations should be documented by the Investigator and images uploaded to the imaging repository, for a possible independent read at a later date. #): C3, C5, C7, C9, C11, C13, C15 and subsequently every 4 cycles until study closure, or disease progression regardless of study intervention modifications/discontinuation. If disease progression is not certain, consider continuing to image.	

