## Follow-up Period

All participants are to be followed up after stop of treatment with tepotinib and cetuximab, including an End of Treatment (EoT) Visit within 14 days of the last dose of tepotinib and/or cetuximab. A Safety Follow-up Visit will occur 30 (- 3 to + 7) days after the last dose of tepotinib and/or cetuximab for all participants who discontinued the study intervention permanently. After the Safety Follow-up Visit, the Survival Follow-up is to be performed every 3 months ( $\pm$ 1 month) at clinic visits or by telephone contact for up to 1 year. Participants' survival information will be collected. Any subsequent anticancer therapy given to the participant until death should be recorded.

Participants who discontinue treatment for reasons other than progressive disease (PD) or death will have additional visits for tumor assessments every 6 weeks until 9 months and every 12 weeks thereafter until disease progression, death, or withdrawal of consent. A  $\pm$  7-day time window is permitted for these additional follow-up visits until 9 months, and  $\pm$  14 days thereafter.

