Cytology results will be collected when available. Enlarging pleural/pericardial effusion and/or ascites (fluid collections) may or may not denote progression. The radiologist can utilize cytology findings (if available) to decide if significant new fluid or unequivocal and significant enlarging fluid is an indication of progression.

The Investigator may perform scans in addition to a scheduled study scan for medical reasons or if the Investigator suspects PD. Participants who withdraw from the study for clinical or symptomatic deterioration before objective documentation of PD will be requested to undergo appropriate imaging to confirm PD. Every effort should be made to confirm a clinical diagnosis of PD by imaging according to RECIST Version 1.1.

Participants will be assessed every 6 weeks starting from Cycle 3 Day 1 visit until 9 months, and every 12 weeks thereafter according to RECIST Version 1.1, until disease progression, death, withdrawal of consent, or study closure. Details on how to perform RECIST Version 1.1

assessments are provided in [Appendix 5](#). Investigator assessments will be conducted. Any CR or PR should be confirmed, preferably at the scheduled 6-week interval or at the next scheduled imaging visit, but no sooner than 4 weeks after the initial documentation of CR or PR. In the case of symptoms suggesting progression, participants should be evaluated by imaging thereafter for documentation and confirmation of the tumor responses.

The same method of assessment and the same technique should be used to characterize each identified and reported lesion at Baseline and during the study. If a chest X-ray indicates metastatic disease while the participant is enrolled in this study, a CT of the chest is required for confirmation. All assessments should be provided by the same physician or radiologist if possible during the study.

Participants who withdraw from the treatment for reasons other than progressive disease will have additional visits for tumor assessments every 6 weeks until 9 months, and every 12 weeks thereafter until disease progression. A  $\pm$  7-day time window is permitted for these additional follow-up visits until 9 months, and  $\pm$  14 days thereafter. Reasons for study termination should be recorded if this visit is the last visit for the participant. Recording of any new anticancer therapy will be made (a tumor assessment is mandatory before initiating the new therapy).

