DoR (months) according to RECIST Version 1.1 assessed by the Investigators.	
For participants with objective response, duration of response is the time from when the CR/PR (whichever is first) criteria are first met until PD or death due to any cause within the period of 2 scheduled tumor assessments (84 or 168 days) after the last tumor assessment, whichever occurs first.
 
Duration of response data will be censored on the date of the last adequate tumor assessment for participants who do not have an event (PD or death) or for participants with an event after the period of 2 scheduled tumor assessments (84 or 168 days) of the last tumor assessment. Participants who do not have a tumor assessment after objective response will be censored at the date CR/PR criteria are first met.
 
Duration of response will be summarized descriptively. Kaplan-Meier plots as well as the corresponding number of events, 1st and 3rd quartile (Q1 and Q3), median, minimum and maximum from the Kaplan-Meier product-limit estimates of the survival function and survival rates at 3, 6, 9, 12, 15, and 18 months together with corresponding 95% CI will be presented.

Endpoint	Statistical Analysis Methods
PFS (months) according to RECIST Version 1.1 assessed by the Investigators.	
Progression free survival is defined as the time (in months) from first administration of study intervention to the date of the first documentation of PD or death due to any cause within the period of 2 scheduled tumor assessments (84 or 168 days) after the last tumor assessment, whichever occurs first.
 
PFS data will be censored on the date of the last evaluable tumor assessment for participants who do not have an event (PD or death) or for participants with an event after the period of 2 scheduled tumor assessments (more than 84 or 168 days) after the last tumor assessment. Participants who do not have a Baseline tumor assessment or who do not have any post Baseline tumor assessments will be censored at the date of the start of study intervention.
 
PFS will be summarized descriptively. Kaplan-Meier plots as well as the corresponding number of events, first and third quartile (Q1 and Q3), median, minimum and maximum from the Kaplan-Meier product-limit estimates of the survival function and survival rates at 3, 6, 9, 12, 15, and 18 months together with corresponding 95% CI will be presented.

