6.2 Interim analysis for futility

A futility analysis will be performed after the first 12 participants are enrolled for second line (2L) treatment (Cohort A). The date 13 weeks after the first dose date (the scheduled time point of the second scan, C5D1, including a time window of 7 days) of the 12th patient enrolled will be used here as cut-off date. Recruitment of further participants into this study, both cohorts, will continue. If there are less than 2 responders (confirmed CR or PR) within the first 12 participants treated with RP2D, the enrolment of 2L participants for this study might be stopped for futility.

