Mean, median, Q1, Q3, Min, and Max will have the same precision as collected in SDTM datasets for non-derived data. Standard deviation will be presented with one digit more than the mean. Percentage and percent change from baseline will be reported using one decimal digit, if not specified otherwise. Derived data such as duration and “time since” variables (see Section 9.4) will be displayed with one decimal digit, unless stated otherwise.

If there are no missing values, the number of participants with missing values should be indicated by a 0.

Qualitative variables will be summarized by frequency counts and percentages. Unless otherwise stated the calculation of proportions will be based on the number of participants in the analysis set of interest. Therefore, counts of missing observations will be included in the denominator and presented as a separate category.

For variables where a participant may have more than one category due to multiple responses per participant, the number of participants included in each category will be summarized as a percentage from all participants. Therefore, the total frequency across categories may not equal the total number of all participants in that analysis group.

Scheduled and unscheduled visits

Data collected at both scheduled and unscheduled visits will be included in the derivation of safety and efficacy endpoints.

Unscheduled visits will be included in the derivation of baseline or worst on-treatment values. Descriptive statistics by nominal visit or time point, e.g. for laboratory measurements, will include only data from scheduled visits

Significance level:

There is no formal significance level for this study, and all analyses are considered descriptive.

There will be no statistical tests performed. If confidence or credibility intervals are mentioned, the level will be 95% unless otherwise specified.

Statistical software:

All analyses will be performed using SAS® Software version 9.4 or higher.

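### The 84/168-day limit for PFS events leaves out the permitted visit windows, so PD found at an in-window scan after one missed or non-evaluable assessment can be censored

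*SAP*

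**What the plan says.** Protocol 9.4.1 counts a PFS or DoR event only "within the period of 2 scheduled tumor assessments (84 or 168 days) after the last tumor assessment, whichever occurs first"; its censoring sentences extend the limit to any event, PD or death. SAP 14.2.2 turns this into a date difference and censors when "date of PD/death - date of last evaluable tumor assessment > 84 or > 168 days". SAP 14.2.1 does the same for DoR ("date of last evaluable tumor assessment > 84 or 168").

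Table 4 in SAP 14.2.2 takes as reference the last CR, PR or SD assessment or the start of treatment. PD or death beyond the limit is censored at the later of those two dates. DoR has no such table. Its reference is the last evaluable assessment, defined as any result other than NE.

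Scan timing comes from Protocol 8.1.1 ("Participants will be assessed every 6 weeks starting from Cycle 3 Day 1 visit until 9 months, and every 12 weeks thereafter") and the schedule in Protocol 1.3 ("C3, C5, C7, C9, C11, C13, C15 and subsequently every 4 cycles until study closure"). On-treatment visits carry a window of 3 days either way (Protocol 1.3). For participants who stop treatment without PD, Protocol 4.1 and 8.1.1 say that a plus or minus "7-day time window is permitted for these additional follow-up visits until 9 months", and 14 days after that.

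**The concern.** A limit of two scheduled assessments is normally meant to tolerate one missed scan and to censor after two. Here the tolerance has no slack. After one missed or NE scan, the next one is due exactly on the limit, so a day's delay that the protocol allows turns a known progression into a censored observation.

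The clearest case is at the start. If C3D1 is missed or NE and PD is seen at C5D1 one day late, the difference from first dose is 85 days. Under Table 4 the participant is censored at treatment start and contributes no follow-up.

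The rule can only remove progressions, never add them. From the date of the affected PD onward, the PFS curve therefore looks better than it would with the event counted. The cohorts have 22 and 20 participants, so one event is visible.

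**Working it through.** **The plan's limits.** 2 x 6 weeks x 7 = 84 days and 2 x 12 weeks x 7 = 168 days. Both reproduce exactly, so no window is included.

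**Nominal gap after one missed scan.** Scan days from first dose are (cycle - 1) x 21: C3 = 42, C5 = 84, C7 = 126, up to C15 = 294, then C19 = 378, C23 = 462.
- First dose to C5: 84 days. C3 to C7: 126 - 42 = 84 days.
- C15 to C23: 462 - 294 = 168 days.

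**Share censored.** Let the offsets of the reference scan and the PD scan be u1 and u2, each between -w and +w days. The gap is nominal + (u2 - u1), so PD is censored when u2 > u1. If the two offsets follow the same distribution independently, the share is (1 - P(u1 = u2))/2. With uniform whole-day offsets (assumption), P(u1 = u2) = 1/(2w + 1).

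| Window | Share censored | Largest in-window gap, one missed | Smallest in-window gap, two missed |
|---|---|---|---|
| ±3 (6-weekly) | (1 - 1/7)/2 = 42.9% | 84 + 6 = 90 | 126 - 6 = 120 |
| ±7 (6-weekly) | (1 - 1/15)/2 = 46.7% | 84 + 14 = 98 | 126 - 14 = 112 |
| ±14 (12-weekly) | (1 - 1/29)/2 = 48.3% | 168 + 28 = 196 | 252 - 28 = 224 |

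Measured from first dose, which has no window, the uniform share is w/(2w + 1): again 3/7 = 42.9% for ±3.

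**Sensitivity to scan timing, scan to scan.** A triangular spread around the due date gives 41.4%, 45.8% and 47.8%. With an extra 50% of scans exactly on the due day the share is 32.1% to 36.2%; with an extra 75% it is 18.8% to 21.1%.

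**Size.** The documents give no missed-scan rate. If 10% of PD events follow one missed scan and all participants progress:
- Cohort A: 22 x 0.10 x 0.429 = 0.94 to 22 x 0.10 x 0.467 = 1.03 events.
- Cohort B: 20 x 0.10 x 0.429 = 0.86 to 20 x 0.10 x 0.467 = 0.93 events.

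A simulation with 6-weekly scans, exponential progression (assumed medians 2.6 to 5.3 months) and 10% of scans missed or NE put 6-month PFS about 0.5 to 1.5 points higher than with windows included. For example, with a median of 122 days and ±7 days it was 41.4% against 39.9%.

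**After the change.** With limits of 98 and 196 days, no in-window PD after one missed scan is censored, and PD after two missed scans still is (112 > 98, 224 > 196). Adding the window once only (87, 91 or 182 days) would still censor about 12%.

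**The case against.** **The days define the period.** Each statement puts the day count beside the words, so this can be read as one pre-specified cut-off and not two conflicting rules. That is fair, and the point does not need a contradiction: followed exactly, the plan still censors PD at a permitted scan after one missed assessment. SAP 6.2 allows for "the scheduled time point of the second scan, C5D1, including a time window of 7 days", but that sets a data cut-off, not an event definition. It shows that the window was considered for this scan; it does not show that 14.2.2 is inconsistent.

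**Almost half of progressions are lost.** A reader might infer this from 43% to 48%. The share applies only to PD after exactly one missed or NE scan, and it rests on an assumed spread of dates.

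**Mitigation.** Protocol 7.3 asks sites to reschedule missed visits as soon as possible, and 8.1.1 allows extra scans when PD is suspected. In a rerun with a median of 122 days, ±3 days and 10% missed, 6-month PFS was 41.1% under the plan and 39.9% with windows. With half of missed scans rescheduled within 3 weeks (assumption) it was 39.6% and 38.9%. This stands and reduces the effect.

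**Precision and bias.** At 40% PFS the 95% half-width is about 1.96 x sqrt(0.24/22) = 20 points in Cohort A and 21 in Cohort B, far more than the shift. Nor is the shift the whole bias: true 6-month PFS in that rerun was 35.4%, so most of the excess comes from scan spacing and missed scans, and the change leaves it in place.

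**DoR.** A reader might assume that the same loss is established for DoR. It is not. Since evaluable means not NE, the PD scan can be its own reference, giving a gap of zero. Only Table 4 settles this, and only for PFS.

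**Conclusion.** The point holds for PFS as SAP 14.2.2 and Table 4 are written. The limit equals the nominal gap after one missed scan, so documented PD inside the visit window is censored if its scan falls later in the window than the reference did. This follows from the documents alone.

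The size depends on assumptions about the spread of scan dates and the missed-scan rate. Roughly one event per cohort or fewer, and about 0.5 to 1.5 points on 6-month PFS, is a reasonable reading at 10% missed. For DoR the effect arises only if the reference scan is read as in Table 4.

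Both endpoints are secondary, and SAP Section 9 states: "There is no formal significance level for this study, and all analyses are considered descriptive". Confirmed ORR, the futility rule and the sample size do not use this limit. It should be corrected because the change is cheap and the loss runs one way; it does not threaten the trial's main conclusion.

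**What to change.** Before database lock, in SAP 14.2.1, 14.2.2 and Table 4 and in Protocol 9.4.1:
- Replace 84 by 98 days (84 + 2 x 7) during 6-weekly scanning and 168 by 196 days (168 + 2 x 14) during 12-weekly scanning. With the ±3-day window alone 90 days would suffice, but one figure of 98 covers on- and off-treatment scans and still excludes PD after two missed scans.
- In 14.2.1, define the DoR reference as the last CR, PR or SD assessment before the event, as Table 4 does for PFS. Align the DoR estimand, which gives 164 days where the text gives 168.
- Do not replace the limit by a count of two or more consecutive missed assessments. That is a different rule for deaths: a death on day 90 after missed scans at days 42 and 84 is an event under 98 days and censored under the count.

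The cost is wording and a programming constant. PD and deaths up to 14 days (6-weekly) or 28 days (12-weekly) beyond the present limits would also count, making PFS and DoR slightly less favourable. Which limit applies to a gap spanning the change of scan interval is a separate question that the same rewrite could settle.

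### SAP 14.2.2 gives two PFS outcomes for a participant who dies within 84 days of first dose with no post-baseline scan: censored at treatment start, or an event

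*SAP*

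**What the plan says.** **Early death, PFS.**
- SAP 14.2.2, text: participants "who do not have any post baseline tumor assessments will be censored at the date of the start of study intervention". Protocol 9.4.1, PFS row, has the same rule: "who do not have any post Baseline tumor assessments will be censored at the date of the start of study intervention". Neither makes an exception for death.
- SAP 14.2.2, next sentence: participants without an evaluable post-baseline assessment are censored at treatment start "unless death occurred within the period of 2 scheduled tumor assessments (84 or 168 days, respectively) after the first dose of study treatment"; in that case the death is an event.
- SAP Table 4, event row: the gap is counted "after last response assessment of CR, PR or SD or start of treatment". Its censoring date is "Date of last tumor assessment with outcome CR, PR or SD or date of start of treatment, whatever is later".
- SAP PFS estimand, endpoint line: "death events occurring within two scheduled tumor assessments after last evaluable assessment or first dose". The intercurrent-event bullet below it leaves out first dose: "Death within two scheduled tumor assessments after last evaluable assessment will be considered as event of interest (composite strategy").

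**Reference date for the gap, PFS and DoR.**
- Protocol 9.4.1 measures the gap from the last tumor assessment, for both endpoints.
- The SAP PFS definition uses two terms in one sentence: "after the last tumor assessment (i.e. time between date of PD/death - date of last evaluable tumor assessment". The SAP DoR definition (14.2.1) has the same pattern. The last evaluable assessment is defined as the last one that is not NE, and SAP 9.9 counts PD as evaluable. Neither place says that the assessment must come before the event.
- Table 4 uses the last CR, PR or SD, or start of treatment. It covers PFS only; DoR has no table.

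**The concern.** The same participant is an event under one instruction and censored under another, and both instructions stand in the same SAP section. If the unconditional rule is programmed, deaths before the first scan leave the risk set at Day 1 and never count. These are the worst outcomes in the study, so the remaining curve looks better than the data. The trial is open-label, so the choice should be fixed before anyone has seen which participants it affects.

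The gap reference raises the same kind of problem on a smaller scale. After an NE scan, the protocol wording and the SAP formula can give different event status and different times.

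**Working it through.** **1. The limit.** Scans are due at C3D1 and C5D1. Visit day = 21 × (cycle − 1) + 1, so these are Day 43 and Day 85. Two scheduled assessments after first dose span 85 − 1 = 84 days, which agrees with 2 × 6 × 7 = 84. The later figure also reproduces: 2 × 12 × 7 = 168. The 164 in the DoR estimand does not. Three months is 3 × 30.4375 = 91.3 days, so every death in question falls before the first reported PFS rate.

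**2. One participant, each rule.** First dose Day 1, no post-baseline scan, death Day 30:

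| Source | Result |
|---|---|
| SAP 14.2.2, unconditional sentence | Censored, Day 1 |
| Protocol 9.4.1 | Censored, Day 1 |
| SAP 14.2.2, next sentence | Event, Day 30 |
| SAP Table 4 | Event, Day 30 |
| PFS estimand, endpoint line | Event, Day 30 |

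Suppose the first sentence is kept for participants with no scan and the second for those with only NE scans. Then Table 4 and the estimand endpoint are contradicted, and a death after an NE scan counts while a death before any scan does not. Suppose instead that the second is an exception to the first. Then the SAP is consistent but departs from the protocol, and SAP Section 7, where changes to the planned analyses belong, covers only COVID-19.

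**3. Size.** Let x of n participants be progression-free at 3 months, with d early deaths and no other censoring before then.
- Deaths as events: S = x/n.
- Deaths censored at Day 1: S = x/(n − d).

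From the last early death onward the second is always the larger.

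| Cohort | x/n | d = 0 censored | d = 1 | d = 2 |
|---|---|---|---|---|
| A | 11/22 | 50.0% | 11/21 = 52.4% | 11/20 = 55.0% |
| A | 7/22 | 31.8% | 7/21 = 33.3% | 7/20 = 35.0% |
| A | 15/22 | 68.2% | 15/21 = 71.4% | 15/20 = 75.0% |
| B | 10/20 | 50.0% | 10/19 = 52.6% | 10/18 = 55.6% |

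The log-log 95% intervals for the first row are 28.2 to 68.4, 29.7 to 70.9, and 31.3 to 73.5. For 11/22:
- SE of log S = √[(1 − 0.5)/(22 × 0.5)] = 0.213.
- Divided by −log 0.5 = 0.693, this gives 0.308 on the log-log scale.
- The limits are exp(−0.693 × e^(±1.96 × 0.308)) = 0.282 and 0.684, a width of 40.2 points.

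**4. Median.** Assume n = 22 and that the other participants progress with an underlying median of 4 months, seen at 6-weekly scans. The estimated median is 4.17 months under both rules for one to three early deaths, and 2.79 against 4.17 months for four. With an assumed 5.2 months it first differs at three deaths (4.17 against 5.55 months).

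**5. Gap reference.** SD Day 43, NE Day 85, death Day 150, limit 84 days:
- From the last tumor assessment (protocol): 150 − 85 = 65 ≤ 84. Event at 150/30.4375 = 4.9 months.
- From the last evaluable assessment (SAP formula) or last CR/PR/SD (Table 4): 150 − 43 = 107 > 84. Censored at 43/30.4375 = 1.4 months.

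**The case against.** The best reply is that the SAP can be read sensibly. The more specific sentence, Table 4 and the estimand endpoint all make the death an event, and a programmer would probably follow the table. Eligibility requires ECOG 0 or 1 and life expectancy over 3 months, so such deaths should be few. All of that is fair. It does not remove the unconditional sentence from the SAP, and it leaves the protocol saying the opposite without a declared departure.

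On the gap reference more of the reply stands. The SAP's formulas already narrow the last assessment to the last evaluable one, and its DoR censoring sentence says so in words. What remains is the protocol's different wording, Table 4's different term, and no statement that the reference precedes the event.

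A reader might infer more than this. Four such readings are not supported:
- **That a PD scan is its own reference, so no PD is ever censored for a gap.** The SAP expressly censors a PD that comes after the gap. That rule would be empty on this reading, so the reference must be meant to precede the event.
- **That the protocol has a further gap reference, the last adequate assessment.** In the DoR row that is the censoring date. The gap in the same sentence is measured from the last tumor assessment.
- **That a 126-day limit applies around C13.** On the Schedule of Activities, C13 (Day 253) to C19 (Day 379) spans 126 days. But Protocol 4.1 and 8.1.1 switch to 12-weekly scans at 9 months (9 × 30.4375 = 273.9, Day 274), before C15D1 (Day 295), and participants off treatment have no cycles. Neither document contains a 126-day limit.
- **That a missing baseline scan is a further conflict.** Both documents censor that case at treatment start. It should not arise, because measurable disease and a baseline scan within 28 days are required and waivers are barred.

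**Conclusion.** The conflict over early deaths is real, and it should be resolved before database lock. Following the unconditional rule biases the reported PFS rates upward: by 2.4 points at 3 months for one such death and 5.0 for two, with 11 of 22 progression-free (2.6 and 5.6 points with 10 of 20 in Cohort B). The documents give neither the number of early deaths nor the PFS distribution, so these figures are illustrations. They are small against the interval, and the median may not change, but the direction is always the same.

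The gap-reference wording is a lesser point of clarification. It matters mainly after NE scans, and the documents do not say how often those will occur.

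PFS and DoR are secondary, and all analyses are descriptive. Objective response and the futility rule are unaffected, because a participant who dies before a confirmed response is a non-responder (SAP 14.1.1). OS counts every death up to the cut-off.

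**What to change.** Before database lock:

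1. In SAP 14.2.2 and the PFS row of Protocol 9.4.1, replace the unconditional Day-1 censoring of participants without post-baseline assessments with the Table 4 rule. A death within two scheduled assessments of first dose is an event; otherwise censor at treatment start. If the protocol is left as it is, declare the departure in SAP Section 7.
2. Add first dose to the intercurrent-event bullet of the PFS estimand, to match its endpoint line.
3. For PFS and DoR, define the gap reference once as the last CR, PR or SD assessment before the event (or first dose, for PFS only), and use that term throughout.
4. State when 84 and when 168 days applies, after reconciling the Schedule of Activities (6-weekly scans to C15) with the 9-month switch in Protocol 4.1 and 8.1.1. Do not set cycle-based or 126-day cut-points.
5. Editorial: the PFS text should point to Table 4, not Table 5; in the DoR estimand change 164 to 168 and remove the reference to first dose, which cannot apply to a confirmed responder.

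The cost is a few SAP lines, plus either a protocol amendment with IRB/IEC approval or a declared departure. No new data are needed. Reported PFS may be slightly shorter if early deaths occur.
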